7.2.3 Missing Date Information for Adverse Events and Concomitant Medications

The following conventions will be used to impute missing portions of dates for adverse events and concomitant medications. Note that the imputed values outlined here may not always provide the most conservative date.

Missing Start Dates

- If the day is unknown, then:
 - If the month and year match the first dose of investigational product start date month and year in this study, then impute the day of the first dose date.
 - Otherwise, assign the first day of the month.
- If the month is unknown, then:
 - If the year matches the year of the first dose of investigational product date in this study, then impute the month and day of the first dose date in this study.
 - Otherwise, assign ‘January’
- If the year is unknown, then the date will not be imputed and will be assigned a missing value.

If the imputed date is earlier than birth date, then birth date will be used

Missing Stop Dates

- If the day is unknown, then assign the last day of the month.
- If the month is unknown, then assign ‘December.’
- If the year is unknown, then the date will not be imputed and will be assigned a missing value.
- If the resulting end date is after the date of study completion / discontinuation/ data cutoff, set the imputed end date as the date of study completion / discontinuation/ data cutoff.

7.2.4 Missing Causal Relationship to Investigational Product for Adverse Events

If the causal relationship to the investigational product is missing for an AE that started on or after the date of the first dose of double-blind investigational product, a causality of “definitely related” will be assigned. The imputed values for causal relationship to investigational product will be used for the incidence summary; the values will be shown as missing in the data listings.

7.2.5 Visit Time Windows

There is no visit time window applied to handle the missing values for a scheduled visit. Nominal scheduled visits will be used for by-visit analyses. If an unscheduled visit has to be used, the principle of proximity will be applied.

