## 7.6 Statistical Methods and Determination of Sample Size

The completeness of the data affects the integrity and accuracy of the final study analysis. Therefore, every effort will be made to ensure complete, accurate and timely data collection, and to avoid missing data. The procedures for handling missing, unused, or spurious data, along with the detailed method for analysis of each variable will be presented in the Statistical Analysis Plan (SAP); the information below is intended as a guide to planned analyses.

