8 STATISTICAL METHODS OF ANALYSES

8.1 General Principles

The statistical analyses will be reported using summary tables, figures, and data listings. Statistical tests, if any, will be 2-sided at the 5% level of significance. All p-values will be presented as nominal p-values. No adjustment on multiplicity will be made. Confidence intervals will be 2-sided 95% confidence intervals, unless stated otherwise. Continuous variables will be summarized by number of subjects and mean, SD / SE, median, minimum, and maximum values. Categorical variables will be summarized by number and percentage. No imputation on missing data will be made, unless stated otherwise.

The final analysis will be conducted when all patients enrolled in the study have completed the Week 48 visit or have discontinued the study.

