8.8 Efficacy Analyses

For each efficacy endpoint, summary statistics will be reported at each visit for the observed measures and their respective changes from baseline.

The efficacy endpoints measured over time will be analyzed using GEE using the Full Analysis Set. Changes from baseline will be the dependent variable, and baseline, visit will be the independent variables in the model. All efficacy endpoints were assessed at Baseline, Week 12, Week 24, Week 36, and Week 48.

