8.9.3 Biomarkers and Drug Concentration Measurements

Serum Creatine Kinase (CK), serum SA, and urine ManNAc will be collected at baseline, week 12, week 24, week 36, and week 48 or termination visit.

- Free SA: Free SA levels in serum assess the drug concentration in the bloodstream resulting from treatment and are the best indicator of compliance with the treatment regimen. Free SA levels in serum are expressed in micrograms of SA per ml of serum
- Creatine Kinase Levels: CK levels in serum will be measured to assess the degree of reduction of CK levels observed as a surrogate for muscle injury.
- Presence of ManNAc: To detect noncompliance with prohibited medication restrictions during the study period.

The changes from baseline will be summarized and analyzed for the duration of the treatment using GEE.

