^m The muscle strength (HHD) assessment will be administered to all subjects. The number of clinical assessments performed at each visit will be determined by the subject's extent of disease involvement. The physical therapist conducting the testing will choose the appropriate number and type of assessments guided by their clinical judgment, study training, and Clinical Evaluator Manual.

ⁿ Lower extremity muscle strength for knee extensors muscle group only.

^o The SF-36 will only be completed for subjects when a validated version is available in the subject's native language.

^p PGI-S (Patient global Impression of Severity) and PGI-C (Patient Global Impression of Change): PGI-S is to be administered only at baseline. PGI-C to be administered at all subsequent visits, including Early Termination.

^q Study drug will be dispensed only after all eligibility requirements are confirmed and study procedures at the Baseline Visit have been performed

^r This Safety Follow-up TC is to be completed only for subjects who complete the study and choose not to enroll in the extension study, UX001-CL302, or who discontinue the study early. This call is not required for subjects who are eligible and choose to take part in Study UX001-CL302. The site personnel should initiate the Safety Follow-up TC 30 (+5) days after a subject's last dose of study drug for subjects who complete the 48-week Treatment Period or 30 (+5) days after the ET Visit or ET TC for subjects who discontinue the study early. Information on any ongoing or new AEs, SAEs, and concomitant medications will be collected. Appropriate follow-up should continue until all safety concerns, in the Investigator's opinion, are resolved.

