10.6 Summary of Efficacy Endpoints and Analyses

Test / Instrument	Endpoint	Type of analysis	Time points for Assessment	Statistical approach at week 48/ET analysis
GNEM Functional Activities Scale (GNEM-FAS) – Expanded Version	Change from baseline in GNEM-FAS Expanded Version total score and mobility, upper extremity and self-care domain scores from baseline over the duration of the study	Secondary efficacy analysis	Baseline, Weeks 12, 24, 36, and 48	GEE Model / Descriptive statistics
Physical therapy – Hand-held Dynamometry (HHD)	Change from baseline in upper extremity strength in the following muscle groups: grip, key pinch, shoulder abductors and wrist extensors over the duration of study	Secondary efficacy analysis	Baseline, Weeks 12, 24, 36, and 48	GEE Model / Descriptive statistics
	Change from baseline in lower extremity muscle strength in the knee extensors as measured by HHD over the duration of the study			
	% of Predicted Normal HHD Values			
Medical Outcome Survey – 36 Items (SF-36)	Change in health-related quality of life as assessed by using SF-36 over the duration of the study	Exploratory efficacy analysis	Baseline, Weeks 12, 24, 36, and 48	GEE Model / Descriptive statistics
Patient Global Impression of Severity & Change (PGI-S & PGI-C)	Change in symptom severity as measured by PGI-S (baseline only) and PGI-C over the duration of the study	Exploratory efficacy analysis	Baseline, Weeks 12, 24, 36, and 48	Descriptive statistics

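### Does the SAP need a rule for which analysis visit an in-clinic Early Termination value takes?

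*SAP*

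**What the plan says.** Protocol 7.6 leaves the detail to the SAP: "The procedures for handling missing, unused, or spurious data, along with the detailed method for analysis of each variable will be presented" there. SAP 7.2.5 applies no visit windows, states that "Nominal scheduled visits will be used for by-visit analyses", and adds: "If an unscheduled visit has to be used, the principle of proximity will be applied". ET is not named.

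Other sections bear on where an ET value belongs.

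- **Towards Week 48.** Protocol 7.5.1.4 treats Week 48 and ET as one visit. The Schedule of Events (Protocol Table 2.1, SAP 10.5) gives them one column. SAP 8.9.3 says that creatine kinase, serum sialic acid (SA) and urine ManNAc "will be collected at baseline, week 12, week 24, week 36, and week 48 or termination visit", and SAP 8.10.4 pairs the two in the same way for physical examinations. A column of the table in SAP 10.6 is headed "Statistical approach at week 48/ET analysis".
- **Towards no visit.** SAP 8.8 says "All efficacy endpoints were assessed at Baseline, Week 12, Week 24, Week 36, and Week 48", and the time-point column of SAP 10.6 lists the same visits. Yet the schedule footnote on the global impression scales has "PGI-C to be administered at all subsequent visits, including Early Termination".
- **Towards the nearest visit.** Only the proximity sentence in SAP 7.2.5, and only if ET counts as unscheduled.

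**The concern.** Visit is a categorical term in the generalized estimating equation (GEE) model (SAP 8.2, 8.8), so the label given to a value affects the estimate. An in-clinic ET can fall at any point in the study, up to four weeks after discontinuation. A measurement taken at Week 8 and labelled Week 48 behaves much like a carried-forward value, in a plan whose default is no imputation (SAP 8.1).

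The study has one arm and no blinding, so a mapping settled late would be settled by people who can see the data. Two side effects could follow. A free SA sample drawn after dosing stopped would dilute the Week 48 concentration summary. And if ET takes no visit, ET laboratory values would drop out of the by-visit statistics in SAP 8.10.2.

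**Working it through.** The SAP gives no figure on this point. Its one design probability (SAP 3.4) reproduces, 1 − 0.9^45 = 0.991 against a stated minimum of 98%, and does not involve ET.

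**Inputs.** Planned N is 45 (SAP 3.4). The only in-document guide to dropout is Protocol 5.2.3: 47 subjects in UX001-CL201, 46 entering the extension. That gives d = 1/47 = 2.1%, or 45 × 0.021 ≈ 1 subject here. Higher rates (d = 10 to 30%, or 4.5 to 13.5 subjects), the decline rates and the within-subject correlation of 0.5 are assumptions. Every dropout is treated as an in-clinic ET at week w.

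**Case 1: dropouts decline linearly, like completers.** With ET coded as Week 48, the expected Week 48 change is multiplied by 1 − d(1 − w/48).

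| d | w=8 | w=16 | w=24 | w=32 | w=40 |
|---|---|---|---|---|---|
| 1/47 | 0.982 | 0.986 | 0.989 | 0.993 | 0.996 |
| 0.10 | 0.917 | 0.933 | 0.950 | 0.967 | 0.983 |
| 0.20 | 0.833 | 0.867 | 0.900 | 0.933 | 0.967 |
| 0.30 | 0.750 | 0.800 | 0.850 | 0.900 | 0.950 |

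For example, at d = 1/47 and w = 8: 1 − 0.0213 × 40/48 = 0.982. The nearest-visit reading (used only if that visit is empty) gives 0.987 to 1.000 over the same grid, and the no-visit reading gives 1.000. A simulation of 150 runs per dropout level (N=45, true change −1.0, ET spread over Weeks 6 to 44) agrees in direction. At 20% dropout the Week 48 estimate is −0.89 with ET as Week 48, −0.98 with nearest visit and −0.99 with no visit.

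**Case 2: dropouts decline three times as fast.** Completers change by −2.0 and dropouts by −6.0 over 48 weeks, with d = 0.20. The truth is 0.8 × (−2.0) + 0.2 × (−6.0) = −2.80.

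| ET week | As Week 48 | Nearest visit | No visit |
|---|---|---|---|
| 8 | −1.80 | −2.05 | −2.00 |
| 16 | −2.00 | −2.10 | −2.10 |
| 24 | −2.20 | −2.20 | −2.20 |
| 32 | −2.40 | −2.28 | −2.20 |
| 40 | −2.60 | −2.30 | −2.30 |

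Week 48 coding is the worst of the three at Weeks 8 and 16, ties at Week 24, and is the best at Weeks 32 and 40. The codings differ by at most 0.30, while every one of them misses the truth by 0.20 to 1.00. With d = 1/47 (truth −2.085), all codings lie between −1.98 and −2.06.

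**Free SA.** If an off-drug ET sample showed no change from baseline and was placed at Week 48, the mean change there would be multiplied by 1 − d, a loss of 2.1% at d = 1/47.

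**The case for a change.** The best argument for acting is that the gap is certain and closing it is cheap. None of the passages that pair ET with Week 48 is a mapping rule. The shared column and the protocol heading say which procedures are performed, and SAP 8.9.3 and 8.10.4 say what is collected or examined. The heading in SAP 10.6 may only name the final analysis, which SAP 8.1 times for when all subjects "have completed the Week 48 visit or have discontinued the study". Under the no-visit reading, a subject whose sole post-baseline value came at ET would enter the Full Analysis Set and yet contribute to no listed visit. Protocol section 5 gives SA a circulating half-life of under an hour, so an off-drug sample says little about exposure.

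The omission stands, and so does the free SA point in principle. Several parts of the argument carry less weight.

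- The readings are not equally supported. ET has its own place in the schedule and a defined set of procedures, so calling it unscheduled is strained. The joint Week 48/ET visit is the most natural nominal label.
- For free SA, SAP 8.9.3 limits the analysis to the duration of treatment and SAP 6.3 requires evaluable levels. Neither is an explicit exclusion of off-drug samples, but both give an analyst grounds for one.
- For laboratory data, the abnormality shift tables in SAP 8.10.2 are not expressly confined to the listed visits, and the adverse event tables and listings remain.
- SAP 7.3 describes data cleaning. It does not describe analysts choosing visit labels after seeing results.
- Subjects who take the telephone ET option supply no efficacy data, so the larger shifts above are upper values. If half of the dropouts used it (an assumption), the 5 to 25% range would fall to about 3 to 15%. At d = 0.30 and Week 8, for instance, 0.15/0.85 × 40/48 = 0.147.

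A nearest-visit rule with two sensitivity analyses would also cost more than it seems. It would repeat at least 14 secondary analyses twice (four functional scale scores, and five muscle groups in two units each), for about one expected subject.

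**Conclusion.** This is a gap that analysts can fill sensibly, and no change to the plan follows. The documents lean towards Week 48 for in-clinic ET values without saying so outright. At the only dropout figure they supply, about 1 subject in 45, the choice moves the Week 48 mean change by under 2% when dropouts decline like completers. When they decline three times as fast, every coding falls between −1.98 and −2.06. That benchmark comes from a less impaired population, so dropout here could be higher. The shift reaches 5 to 25% only with 10 to 30% dropout, all seen in clinic and leaving by Week 24.

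Even then no coding is shown to be the right one. Which is closest depends on when subjects leave and how fast they decline, and if dropouts decline faster, the error common to all codings is generally larger than the difference between them. The primary adverse event endpoint does not depend on visit labels. Efficacy is secondary or exploratory, unpowered (SAP 3.4) and reported with nominal p-values (SAP 8.1). Prescribing a nearest-visit rule would exchange one arguable convention for another.

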7.3 Testing/Validation Plan

Data will be reviewed by cross functional team periodically and issues will be addressed by clinical data management.

7.4 Software

SAS[®] software version 9.4 or higher will be used to perform all statistical analyses.

8 STATISTICAL METHODS OF ANALYSES

8.1 General Principles

The statistical analyses will be reported using summary tables, figures, and data listings. Statistical tests, if any, will be 2-sided at the 5% level of significance. All p-values will be presented as nominal p-values. No adjustment on multiplicity will be made. Confidence intervals will be 2-sided 95% confidence intervals, unless stated otherwise. Continuous variables will be summarized by number of subjects and mean, SD / SE, median, minimum, and maximum values. Categorical variables will be summarized by number and percentage. No imputation on missing data will be made, unless stated otherwise.

The final analysis will be conducted when all patients enrolled in the study have completed the Week 48 visit or have discontinued the study.

8.2 Repeated Measure Model: General Estimating Equations

The efficacy endpoints are collected over time and will be analyzed using a generalized estimation equation (GEE) model that includes time as the categorical variable and adjusted for baseline measurement. The covariance structure that will be used for the GEE model is compound symmetry which specifies constant variance for the assessments and constant covariance between the assessments over time. If the compound symmetry covariance structure leads to non-convergence, Quasi-Likelihood Information Criterion (QIC) will be used to select the best covariance structure. Model based estimates of the changes from baseline and corresponding 95% confidence intervals will also be provided along with p-values for assessing statistical significance.

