#### 7.6.4 Efficacy Analysis

Baseline values for each endpoint will be defined as the last scheduled data collection visit before beginning treatment according to the Schedule of Events ([Table 2.1](#)). Dynamometry will be administered at the Screening visit to determine eligibility and introduce subjects to performance testing to minimize training effects and will not be used for analysis purposes.

Efficacy analyses will be based on the Full Analysis Set. Generalized estimating equation (GEE) analysis will be performed to assess the changes from baseline of all efficacy endpoints with repeated measurements. Baseline will be included as a covariate in the model.

The statistical analyses will be reported using summary tables, figures, and data listings. Statistical tests will be 2-sided at the alpha =0.05 significance level. All analyses and tabulations will be performed using SAS®. Continuous variables will be summarized with means, standard deviations, medians, minimums, and maximums. Categorical variables will be summarized by counts and by percentages of subjects in corresponding categories. The final analysis will be conducted at Week 48.

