4.4 Covariate(s)

All models used for each individual clinical endpoint will incorporate the baseline value as a covariate.

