7.2 Handling of Missing and Incomplete Data

Missing clinical outcome data can occur for multiple reasons, including missed subject visits and scales or measures with missing item scores. Missing and incomplete data will be identified through a review of tables and listings for this study. Missing and incomplete data will be identified for investigation, and possible resolution, by Data Management prior to the study database lock.

Missing or invalid safety events and assessments will not be imputed or replaced. Missing measurements in HHD individual muscle group test will be imputed as 0 if the reason for missing is due to weakness. When the measurement for one side is missing, the measurement from the other side will be used to impute the missing value. Details of missing observation handling in HHD are provided in Appendix 10.3. Other efficacy endpoints will not be imputed.

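### Does SAP 8.2 need to name the standard error and reference distribution behind its GEE confidence intervals?

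*SAP*

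**What the plan says.** Protocol 7.6.4 sets the method: "Generalized estimating equation (GEE) analysis will be performed to assess the changes from baseline of all efficacy endpoints with repeated measurements". SAP 8.8 gives the model: "Changes from baseline will be the dependent variable, and baseline, visit will be the independent variables in the model". SAP 4.4 repeats the adjustment for baseline: "All models used for each individual clinical endpoint will incorporate the baseline value as a covariate".

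SAP 8.2 fixes the working covariance ("The covariance structure that will be used for the GEE model is compound symmetry which specifies constant variance for the assessments") and changes it only under one condition: "If the compound symmetry covariance structure leads to non-convergence, Quasi-Likelihood Information Criterion (QIC) will be used to select the best covariance structure". On output it says: "Model based estimates of the changes from baseline and corresponding 95% confidence intervals will also be provided along with p-values".

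Nothing else in SAP 8.1, 8.8, 8.9 or 10.6, or in Protocol 7.6.4 and 7.6.5, states whether standard errors are empirical or model-based, whether the reference is normal or t, or whether a small-sample correction applies. SAP 7.4 names SAS but no procedure or option.

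The status of these analyses is stated clearly. SAP 3.4 says the study is not powered for efficacy changes. SAP 8.1 makes all p-values nominal without multiplicity adjustment and treats testing as optional: "Statistical tests, if any, will be 2-sided at the 5% level of significance". SAP 8.10 analyses the primary safety endpoint descriptively.

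**The concern.** A GEE tolerates a wrong working covariance only if its standard errors are empirical. With model-based errors, the interval at each visit uses a variance pooled over the four post-baseline visits. If the SD of change grows over time, the Week 48 interval is too narrow and the Week 12 interval too wide; if the SD shrinks, the reverse holds. Because model-based is also the usual name for the non-robust GEE standard error, the output sentence in SAP 8.2 can be read as choosing it.

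Constant variance cannot be assumed in a progressive disease, particularly for dynamometry, where SAP 7.2 says: "Missing measurements in HHD individual muscle group test will be imputed as 0 if the reason for missing is due to weakness". Even with empirical errors, an uncorrected sandwich estimator with normal critical values under-covers slightly in about 45 subjects. A further point is that, with one arm and a baseline covariate, an interval evaluated at the sample-mean baseline omits the sampling error of that mean.

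At stake are the intervals and p-values for GNEM-FAS and muscle strength, and for the SF-36, PGI-C and biomarker analyses that use the same model. If the choice of error were left until the data had been seen, it would be an avoidable freedom in an open-label study.

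**Working it through.** **The plan's own figure.** No figure is stated for the GEE intervals. The only sizing figure is in SAP 3.4: at least 98% probability of one or more related SAEs at a 10% rate with N=45. This reproduces: 1 − 0.9^45 = 0.9913.

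**Inputs.** From the documents: one arm, about 45 subjects, four post-baseline visits (Weeks 12, 24, 36, 48), compound symmetry, two-sided 95% intervals. The documents give no visit SDs or correlations, so those below are assumptions.

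**Step 1: which reading of SAP 8.2?**
- SAP 8.8 first promises summary statistics at each visit for observed values and changes, then the GEE.
- SAP 8.2 says the model-based estimates are *also* provided, that is, in addition to those summaries.
- SAP 8.9.2 draws the same contrast for PGI-C, between summary statistics and GEE estimates.
- SAP 10.6 pairs the GEE model with descriptive statistics.

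Together these make model-based mean obtained from the GEE. The sentence does not name a variance estimator.

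**Step 2: empirical errors, normal reference, N=45.** For a single mean with complete data the sandwich variance divides by n, so coverage = P(|t44| < 1.96 × √(44/45)) = P(|t44| < 1.938) = 94.1%. Using a t reference changes the critical value from 1.960 to 2.015, an interval 2.8% wider.

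**Step 3: model-based errors.** With complete data and no link to baseline, coverage at Week 48 = 2Φ(1.96 × √(mean of the four visit variances / Week 48 variance)) − 1. For example, if the SD doubles only at Week 48, the mean variance is (1+1+1+4)/4 = 1.75, 1.96 × √(1.75/4) = 1.296, and coverage is 80.5%.

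| Week 48 / Week 12 SD | Change complete by Week 24 | Linear | Only at Week 48 |
|---|---|---|---|
| 0.7 | 97.2% | 98.4% | 99.1% |
| 1.0 | 95.0% | 95.0% | 95.0% |
| 1.5 | 93.1% | 90.1% | 86.6% |
| 2.0 | 92.3% | 87.0% | 80.5% |

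**Step 4: simulation.** Exchangeable GEE on change with baseline as covariate, N=45, correlation 0.6, SD rising linearly where it rises, 2,500 trials per row (Monte Carlo error about 0.4 to 0.7 points). Week 48 coverage:

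| Scenario | Model-based, z | Sandwich, z | Sandwich, t | Mancl-DeRouen, t |
|---|---|---|---|---|
| Constant SD | 94.7% | 94.0% | 94.5% | 95.6% |
| SD up 1.75-fold | 88.6% | 94.4% | 95.0% | 95.7% |
| SD doubled | 86.2% | 93.3% | 94.2% | 95.0% |
| SD doubled, 20% random dropout | 85.3% | 94.1% | 94.9% | 96.0% |

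Across these rows the ordinary sandwich interval covers 93.3% to 94.4% whatever the SD trend. The losses in the first column require the other reading of SAP 8.2.

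**Step 5: baseline mean.** Assume equal SDs at baseline and follow-up and correlation ρ. The squared correlation of change with baseline is then (1 − ρ)/2, and the limit in Step 2 is multiplied by √(1 − (1 − ρ)/2). At ρ = 0.9: 1.938 × √0.95 = 1.889, coverage 93.5%. At ρ = 0.8: 1.938 × √0.90 = 1.839, coverage 92.7%. This applies only to an interval for a wider population's mean change. For an interval conditional on the observed baselines, an ordinary reading of a baseline-adjusted model, the term is absent.

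**The case for a change.** The best case for amending the plan runs as follows. Protocol 7.6 defers analysis detail to the SAP, so SAP 8.2 is where the standard error should be stated, and a software default is not a pre-specified choice. Protocol 7.5.3 bases efficacy conclusions on change from baseline, and the GEE is the planned inference for it. Calling p-values nominal excuses the lack of multiplicity control, but not an interval labelled 95% that covers less. Some endpoints may also have fewer than 45 subjects: the SF-36 needs a validated version in the subject's language, and knee extensors are tested only in subjects who can be positioned properly. With 20 subjects and constant SD, the uncorrected sandwich interval covered 92.2% in simulation. Two sentences would settle the matter.

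The omission stands, and the arithmetic is right. The consequence is what falls short. Once the output sentence is read with the sections around it, what remains is about one point of coverage at 45 subjects and about three at 20. The steep losses depend on SD paths with no source in the documents, and even the direction is open. Zero imputation for weakness applies to dynamometry only and could widen or compress the spread.

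Adding a one-sample t interval to the by-visit tables would gain little, because SAP 8.1 and 8.8 already provide n, mean and SD or SE, from which it can be computed. It would also put a second, available-case interval beside the GEE interval for the same quantity without saying which governs. Restoring the missing point of coverage has a small price too: with constant SD, the Mancl-DeRouen interval with a t reference had width 0.610 against 0.571 for the uncorrected sandwich interval, about 7% wider.

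**Conclusion.** No change to the plan follows. The SAP leaves a programming detail unwritten, and the conventional way of filling it, empirical standard errors for the GEE, gives about 94% coverage for a nominal 95% interval at 45 subjects. That holds whether the SD of change is constant or doubles linearly by Week 48. The shortfall is about one point, on endpoints that are unpowered, have nominal p-values, feed no success rule and come from a study without a control arm (Protocol 7.2). The primary safety endpoint and the sample size are untouched.

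This rests on three things: the reading of SAP 8.2 set out above; near-complete data from about 45 subjects, since smaller subsets lose somewhat more; and assumed SDs and a correlation of 0.6, because the documents give none. It would fail if the programmer used non-robust errors and the SD of change varied materially by visit. A line in the programming specification is enough to prevent that.
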